6.2. Exposure

6.2.1. Analysis of exposure planned in the protocol

None

6.2.2. Additional considerations

The number of doses administered will be tabulated. The number of doses administered will be tabulated by age sub-group.

6.3. Immunogenicity

6.3.1. Analysis of immunogenicity planned in the protocol

The primary analysis will be based on the *Per-protocol set (PPS) for immunogenicity*. A second analysis based on the Exposed set will be performed to complement the per-protocol analysis (see section 9 for changes in the planned analysis).

Immunogenicity analyses for confirmatory objectives will be performed by age stratum (50-59, 60-69 and \geq 70 YOA) on PPS, if the number of subjects enrolled is sufficient in each stratum.

204487 (ZOSTER-059 PRI) Statistical Analysis Plan Amendment 3

6.3.1.1. Within group assessment

The following parameters will be tabulated by vaccine group at each time point when a blood sample result is available:

- Seropositivity with exact 95% CI for all antigens
- GMC/GMT with 95% CI for all antigens
- VRR with exact 95% CI for anti-gE
- Mean Geometric Increase (MGI) with exact 95% CI for anti-gE
- Descriptive statistics (N, mean, SD, min, Q1, median, Q3, max) of Mean Geometric Increase (MGI) for anti-gE
- Distribution of the fold increase i.e. Percentage of subjects with a more than X-fold (e.g. >2, >4, >6, -fold) increase will be tabulated for anti-gE per group with 95% CI.
- Antibody titre/concentration will be displayed using reverse cumulative curves.

6.3.1.2. Between group assessment

The following between group comparison will be performed:

- For the second co-primary objective for non-inferiority of the anti-gE humoral response, at one-month post-dose 2 of HZ/su vaccine:
 - The 95% CI of the group GMCs ratio (Control divided by Co-Ad) will be computed using an ANCOVA model on the log10 transformation of the concentrations. The pre-vaccination log-transformed antibody concentrations will be included as continuous covariate and the vaccine group and age strata as fixed effects in the model.
- For the third co-primary objective for non-inferiority of the humoral response to each vaccine pneumococcal serotype (according to the pre-specified order in the protocol), one month post-dose of *Prevenar13*:
 - The 95% CI of the group MOPA GMT ratios (Control divided by Co-Ad) will be computed using an ANCOVA model on the log10 transformation of the concentrations. The pre-vaccination log-transformed antibody concentrations will be included as continuous covariate and the vaccine group and age strata as fixed effects in the model.

6.3.2. Additional considerations

The following additional points need to be considered for immunogenicity analysis:

- Percentage of subjects above the pneumococcal serotype specific LLOQ will be calculated for each serotype with exact 95% Cis.
- Immunogenicity descriptive analyses will be performed by age stratum (50-59, 60-69 and \geq 70 YOA), if the number of subjects enrolled is sufficient in each stratum.

204487 (ZOSTER-059 PRI) Statistical Analysis Plan Amendment 3

- Two-sided 95% CIs for Seropositivity and VRR will be computed by Clopper-Pearson method [Clopper, 1934].
- The two-sided 95% CI for the mean of log-transformed titre/concentration will be first obtained assuming that log-transformed values were normally distributed with unknown variance. The 95% CI for the GMTs/GMCs/MGIs will be then obtained by exponential-transformation of the 95% CI for the mean of log-transformed titre/concentration.

6.3.2.1. Statistical considerations for confirmatory objectives

For the multiplicity adjustment, all hypotheses have been ranked into three families and one sub-family according to the following power of test:

Table 4 Power to demonstrate VRR objective and non-inferiority of the immunogenicity of HZ/su and *Prevenar13* co-administered compared to Control group

Endpoint	Threshold	VR assumed	Total β	Power
VRR in Co-Ad group	0.60	95%	0.001%	99.99%
Family 2: HZ/su: non-inferi				
Endpoint	Standard deviation	δ	Total β	Power
Anti-gE GMC ratio	0.35	1.5	0.001 %	99.99 %
Family 3: Prevenar13: Non	-inferiority* (1-sided test	with alpha = 2.5%)	N=410	
Endpoint (13 vaccine pneumococcal serotypes)	Standard deviation	δ	Total β	Power
3 GMT ratio	0.660	2	0.001%	99.99%
19A GMT ratio	0.644	2	0.001%	99.99%
1 GMT ratio	0.798	2	0.029%	99.97%
18C GMT ratio	0.891	2	0.203%	99.80%
4 GMT ratio	0.906	2	0.260%	99.74%
6A GMT ratio	0.919	2	0.320%	99.68%
5 GMT ratio	0.931	2	0.383%	99.62%
19F GMT ratio	0.971	2	0.664%	99.33%
6B GMT ratio	0.995	2	0.891%	99.11%
7F GMT ratio	1.014	2	1.107%	98.89%
9V GMT ratio	1.021	2	1.194%	98.81%
14 GMT ratio	1.045	2	1.530%	98.47%
23F GMT ratio	1.094	2	2.398%	97.60%
Global β to show non-inferio	ority		~9%	
Global power	~91%			

VRR: vaccine response rate; gE: Varicella Zoster Virus glycoprotein E; GMT: geometric mean titer; GMC: geometric mean concentration.

For gE: non-inferiority limit = 0.176 (=log10(1.5)), power under equal GMC

For each pneumococcal serotype: non-inferiority limit = 0.301 (=log10(2)), variability for each of the 13 vaccine pneumococcal serotype taken from the EMA assessment report for *Prevenar13* and multiplied by 1.1, power under equal GMT.

^{*} Pass 12, alpha = 2.5%, for VRR: Exact test, for non-inferiority one-sided equivalence of means.

204487 (ZOSTER-059 PRI) Statistical Analysis Plan Amendment 3

Fixed sequence testing which allows for full alpha propagation in pre-ordered hypotheses families will be applied in the following manner:

Family 1:

In the Co-Ad group, for anti-gE, at one month post-dose 2 of HZ/su vaccine:

• The VRR and 95% CI will be computed.

The objective is met if the LL of the 95% CI is \geq 60%.

Family 2:

For anti-gE, at one month post-dose 2 of HZ/su vaccine:

• The 95% CI of the group GMCs ratio will be computed using an analysis of covariance (ANCOVA) model on the log10 transformation of the concentrations. The pre-vaccination log-transformed antibody concentrations will be included as continuous covariate and the vaccine group and age strata as fixed effects in the model.

In terms of concentrations, the Co-Ad group will be considered non-inferior to the Control group if the UL of the 95% CI for the GMC ratio of the Control group to the Co-Ad group is <1.5.

Family 3:

For each vaccine pneumococcal serotype (according to the pre-specified order), one month post-dose of *Prevenar13*:

The 95% CI of the group MOPA GMT ratios will be computed using an analysis of covariance (ANCOVA) model on the log10 transformation of the concentrations.
 The pre-vaccination log-transformed antibody concentrations will be included as continuous covariate and the vaccine group and age strata as fixed effects in the model

In terms of MOPA GMTs, the Co-Ad group will be considered non-inferior to the Control group if the UL of the 95% CI for the MOPA GMTs ratio of the Control group to the Co-Ad group is <2 for each of the 13 vaccine serotypes.

In the ANCOVA models Adjusted Least Squares (LS) means and difference of LS means between the groups will be calculated together with the 2-sided 95% CIs and backtransformed to the original units to provide GMCs and GM ratios.

204487 (ZOSTER-059 PRI) Statistical Analysis Plan Amendment 3

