Rationale/background for changes: Major change: 
• This amendment is in response to the Center for Biologics Evaluation and Research (CBER) comments on Protocol Amendment 1, received on 09-January-2018, requesting clarification on 1. the adjustment for baseline titers in the computation of the Multiplex Opsonophagocytosis Assay (MOPA) Geometric Mean Titers (GMT) ratios (Section 10.7.2) and 2. time points for primary evaluations on co-primary immunogenicity objectives (Section 10.10.1). Other changes: 
• The tradename for pneumococcal polysaccharide conjugate vaccine (13-valent adsorbed) in Canada has been corrected to Prevnar13 from Prevenar13.• The laboratory to be used for MOPA testing has been selected and is presented in Appendix B.• A typographical error in the estimated number of subjects in each age strata and study group has been corrected. Table 4 reflects the correct number of subjects for age stratification.

CONFIDENTIAL204487 (ZOSTER-059 PRI)
Protocol Amendment 2 Final

Protocol Amendment 2 Investigator Agreement

I agree:

- To conduct the study in compliance with this protocol, any future protocol amendments or protocol administrative changes, with the terms of the clinical trial agreement and with any other study conduct procedures and/or study conduct documents provided by GlaxoSmithKline (GSK) Biologicals.
- To assume responsibility for the proper conduct of the study at this site.
- That I am aware of, and will comply with, 'Good Clinical Practice' (GCP) and all applicable regulatory requirements.
- To ensure that all persons assisting me with the study are adequately informed about the GSK Biologicals' study vaccine(s) and other study-related duties and functions as described in the protocol.
- To acquire the reference ranges for laboratory tests performed locally and, if required by local regulations, obtain the laboratory's current certification or Quality Assurance procedure manual.
- To ensure that no clinical samples (including serum samples) are retained onsite or elsewhere without the approval of GSK Biologicals and the express written informed consent of the subject and/or the subject's legally acceptable representative.
- To perform no other biological assays on the clinical samples except those described in the protocol or its amendment(s).

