5.2.2.2.1. Study group and treatment number allocation

The target will be to enrol approximately 912 eligible subjects who will be randomly assigned to two study groups in a 1:1 ratio (approximately 456 in each study group).

The enrolment will be performed to ensure distribution of the population across the three age strata (50-59 YOA, 60-69 YOA and ≥ 70 YOA). Therefore the expected distribution of subjects is as shown in [Table 5](#).

Age will be calculated as the number of years between the date of birth and the date of first vaccination. To ensure that the collection of date of birth will not jeopardise the privacy of Personally Identifiable Information (PII), only a partial date of birth* (MMYYYY) will be collected. Therefore, the 15th of the month will be used to replace the missing date.

In case the month is missing, the date will be replaced by the June 30th of the year.

* In Germany, as per local regulations, only the year of birth will be collected.

CONFIDENTIAL204487 (ZOSTER-059 PRI)
Protocol Amendment 2 Final**Table 5** **Number of subjects required for enrolment**

Age Stratum	Vaccine	N
50-59 YOA	HZ/su	342
	Prevenar13	
60-69 YOA	HZ/su	342
	Prevenar13	
≥ 70 YOA	HZ/su	228
	Prevenar13	

N = number of subjects to be enrolled

Allocation of the subject to a study group at the investigator site will be performed using SBIR. Within each age strata (50-59 YOA, 60-69 YOA and ≥ 70 YOA), the randomization algorithm will use a minimisation procedure accounting for centre.

After obtaining the signed and dated ICF from the subject and having checked the eligibility of the subject, the study staff in charge of the vaccine administration will access SBIR. Upon providing the age (50-59 YOA, 60-69 YOA and ≥ 70 YOA) at the time of enrolment in the study and the subject identification number, the randomization system will determine the study group and will provide the treatment number(s) to be used for the first dose.

The number of each administered treatment must be recorded in the eCRF on the Vaccine Administration screen.

When SBIR is not available, please refer to the SBIR user guide or the Study Procedures Manual (SPM) for specific instructions.

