The global power to meet all co-primary objectives with 410 evaluable subjects in Co-Ad and Control groups is approximately 91% (Table 23). Assuming that about 10% of the subjects enrolled are non-evaluable (e.g. due to dropout, bad sample), approximately 912 subjects will need to be enrolled (456 subjects in each treatment group).

CONFIDENTIAL

204487 (ZOSTER-059 PRI)
Protocol Amendment 2 Final**Table 23 Power to demonstrate VRR objective and non-inferiority of the immunogenicity of HZ/su and *Prevenar13* co-administered compared to Control group**

Family 1: HZ/su: VVR*(1-sided test with alpha = 2.5%)				
Endpoint	Threshold	VR assumed	Total β	Power
VRR in Co-Ad group	0.60	95%	0.001%	99.99%
Family 2: HZ/su: non-inferiority* (1-sided test with alpha = 2.5%) N=410				
Endpoint	Standard deviation	δ	Total β	Power
Anti-gE GMC ratio	0.35	1.5	0.001 %	99.99 %
Family 3: Prevenar13: Non-inferiority* (1-sided test with alpha = 2.5%) N=410				
Endpoint (13 vaccine pneumococcal serotypes)	Standard deviation	δ	Total β	Power
3 GMT ratio	0.660	2	0.001%	99.99%
19A GMT ratio	0.644	2	0.001%	99.99%
1 GMT ratio	0.798	2	0.029%	99.97%
18C GMT ratio	0.891	2	0.203%	99.80%
4 GMT ratio	0.906	2	0.260%	99.74%
6A GMT ratio	0.919	2	0.320%	99.68%
5 GMT ratio	0.931	2	0.383%	99.62%
19F GMT ratio	0.971	2	0.664%	99.33%
6B GMT ratio	0.995	2	0.891%	99.11%
7F GMT ratio	1.014	2	1.107%	98.89%
9V GMT ratio	1.021	2	1.194%	98.81%
14 GMT ratio	1.045	2	1.530%	98.47%
23F GMT ratio	1.094	2	2.398%	97.60%
Global β to show non-inferiority			~9%	
Global power				~91%

VRR: vaccine response rate; gE: Varicella Zoster Virus glycoprotein E; GMT: geometric mean titer; GMC: geometric mean concentration.

* Pass 12, alpha = 2.5%, for VRR: Exact test, for non-inferiority one-sided equivalence of means.

For gE: non-inferiority limit = 0.176 (=log₁₀(1.5)), power under equal GMC

For each pneumococcal serotype: non-inferiority limit = 0.301 (=log₁₀(2)), variability for each of the 13 vaccine pneumococcal serotype taken from the EMA assessment report for *Prevenar13* and multiplied by 1.1, power under equal GMT.

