10.7.2. Statistical considerations for confirmatory objectives

All analyses will be performed overall and by age stratum, if the number of subjects enrolled is sufficient in each stratum.

For the multiplicity adjustment, all hypotheses will be ranked into three families and one subfamily according to the power of test (Table 23). Fixed sequence testing which allows for full alpha propagation in pre-ordered hypotheses families will be applied in the following manner:

Family 1:

In the Co-Ad group, for anti-gE, at one month post-dose 2:

- The VRR and 95% CI will be computed.

The objective is met if the LL of the 95% CI is $\geq 60\%$.

CONFIDENTIAL204487 (ZOSTER-059 PRI)
Protocol Amendment 2 FinalFamily 2:

For anti-gE, at one month post-dose 2:

- The 95% CI of the group GMCs ratio will be computed using an analysis of covariance (ANCOVA) model on the log₁₀ transformation of the concentrations. The pre-vaccination log-transformed antibody concentrations will be included as continuous covariate and the ANCOVA model will include the vaccine group and age strata as fixed effects.

In terms of concentrations, the Co-Ad group will be considered non-inferior to the Control group if the UL of the 95% CI for the GMC ratio of the Control group to the Co-Ad group is <1.5.

Family 3:

For each vaccine pneumococcal serotype (according to the order in [Table 23](#)), one month post-dose:

- The 95% CI of the group MOPA GMT ratios will be computed using an ANCOVA model on the log₁₀ transformation of the titers. ***The pre-vaccination log-transformed antibody titers will be included as a continuous covariate.*** The ANCOVA model will include the vaccine group and age strata as fixed effects. **(Amended 30 January 2018)**

In terms of MOPA GMTs, the Co-Ad group will be considered non-inferior to the Control group if the UL of the 95% CI for the MOPA GMTs ratio of the Control group to the Co-Ad group is <2 for each of the 13 vaccine serotypes.

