10.10. Conduct of analyses

Any deviation(s) or change(s) from the original statistical plan outlined in this protocol will be described and justified in the final study report.

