9. CHANGES FROM PLANNED ANALYSES

- In Protocol Amendment 2 Final (30 Jan 2018), it was specified that a second analysis for immunogenicity of the ES would be performed only if, in any study group, the percentage of enrolled subjects with serological results excluded from the PPS for immunogenicity is 5% or more. At the request of Paul Ehrlich Institute, Germany (PEI), an analysis of the ES will be performed to complement the per-protocol analysis regardless of the percentage of enrolled subjects excluded from the PPS for immunogenicity.
- Updated LLOQ values (i.e. assay cut-off values) for the pneumococcal serotypes are provided in this version of SAP (section 12.1.2). The cut-off values presented in this SAP will be used to determine seropositivity rather than those presented in Protocol Amendment 2 Final (30 Jan 2018). Analysis of immunogenicity section has been updated accordingly.
- Additional tables on presentation of grade 3 non-serious unsolicited adverse events and fatal SAEs has been added based on CBER request.
- The sequence of analysis was updated from SAP amendment 1 to accommodate a delay in the availability of immunogenicity results. The active phase analysis has been removed as a request for a CTRS posting extension has been submitted to NIH; complete CTRS posting will be done at Last Subject Last Visit (LSLV) + 12 months rather than Primary Completion Date (PCD) +12 months as previously planned
- Two new cohorts Enrolled Set and Randomized Set has been defined as required for web disclosure and SAE tables presentation.
- Analysis of demography section has been updated to add consort table and summary of important protocol deviations.

204487 (ZOSTER-059 PRI) Statistical Analysis Plan Amendment 3

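### Centre is a minimisation factor but is left out of the Family 2 and 3 ANCOVAs; if centre is prognostic, the confidence intervals are slightly conservative

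*SAP*

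**What the plan says.** Protocol 4.1 stratifies the randomisation by three age strata. Protocol 5.2.2.2.1 adds that, within each stratum, "the randomization algorithm will use a minimisation procedure accounting for centre". The two statements are compatible: age is stratified and centre is minimised.

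For the anti-gE GMC ratio (Family 2), Protocol 10.7.2 takes log baseline as a covariate and says "the ANCOVA model will include the vaccine group and age strata as fixed effects". The serotype GMT ratios (Family 3) use the same terms. SAP Amendment 3 repeats this in 6.3.1.2 ("vaccine group and age strata as fixed effects in the model") and in 6.3.2.1 ("the vaccine group and age strata as fixed effects in the model"). The footnotes to SAP Templates 30 and 31 list group, age and baseline, with pooled variance.

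Centre appears elsewhere only in descriptive tabulations such as SAP Template 1. The one complementary immunogenicity analysis (SAP 6.3.1) changes the population to the Exposed Set, not the model. SAP section 9, "CHANGES FROM PLANNED ANALYSES", does not mention centre.

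**The concern.** The plan adjusts for one allocation factor (age) and drops the other (centre) without a reason. Minimisation makes the groups similar within centre, so differences between centres contribute little to the chance variation of the group comparison. A model without centre still counts those differences as residual noise. If centre predicts titre after baseline and age are accounted for, the model's standard error exceeds the real standard deviation of the estimate, and the interval is wider than it needs to be.

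Fourteen ratios are affected: one for anti-gE and 13 for serotypes. Each is judged by an upper confidence limit, and the trial is conclusive only if every criterion is met. What is at stake is the width of those intervals, not the validity of a positive result.

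**Working it through.** **1. The plan's own power figure.** Inputs from Protocol 10.3 and Table 23 (repeated in SAP Table 4): 410 evaluable per group, one-sided 2.5%, true ratio 1, log10 SDs as tabulated, margins 0.301 and 0.176. Power = Φ(margin / (SD·√(2/410)) − 1.96).

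- Serotype 23F: SE = 1.094 × 0.0698 = 0.0764. Then 0.301/0.0764 − 1.96 = 1.98, which gives 97.6% (stated 97.60%).
- The β values in the table sum to 8.98%, so global power is 91.0%; multiplying the powers gives 91.3%. The Protocol says "The global power to meet all co-primary objectives with 410 evaluable subjects in Co-Ad and Control groups is approximately 91" per cent, so the figure reproduces.
- These SDs carry no reduction for centre, so the stated power does not depend on centre being modelled.

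**2. Upper bound on the excess width.** Let ρ be the share of residual variance due to centre. The documents give no value, so 2%, 5% and 10% are assumed. With perfect balance the estimate's true SD shrinks by √(1−ρ) while the reported SE does not, so the excess is 1/√(1−ρ) − 1: 1.0%, 2.6% and 5.4%.

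**3. Simulation with realistic imbalance.** 820 subjects; age strata 37.5/37.5/25%; minimisation by centre within stratum (biased coin 0.8); unequal centres; own baseline in both models; residual SD 1; 10,000 trials per cell. The coin and the number of centres are assumptions. The reported SE of the planned model is about 2/√820 = 0.0698.

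| ρ | True SD, 15/30/60 centres | Mean | 0.0698/mean − 1 | Coverage, planned / with centre | One-sided error, planned / with centre |
|---|---|---|---|---|---|
| 2% | 0.0706 / 0.0683 / 0.0693 | 0.0694 | 0.6% | 95.1% / 94.9% | 2.49% / 2.59% |
| 5% | 0.0688 / 0.0686 / 0.0684 | 0.0686 | 1.7% | 95.3% / 94.9% | 2.43% / 2.62% |
| 10% | 0.0671 / 0.0672 / 0.0670 | 0.0671 | 4.0% | 95.9% / 95.0% | 2.12% / 2.57% |

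The Monte Carlo error is about 0.7% on each SD (1/√20,000) and 0.09 points on each one-sided error, so the 2% row cannot be told from no effect. At 10% with 30 centres, the simulated mean SE of 0.0697 against an SD of 0.0672 gives 3.7%.

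A separate simulation minimised 912 subjects and analysed 820, as the plan does, with 30 centres assumed. At ρ = 10% the planned SE was about 5% above the true SD, and coverage was about 96.5% against about 95% with centre. A shorter check of 4,000 runs gave 3.3% and coverage of 95.7%; its Monte Carlo error is about 1.1% (1/√8,000). A fair summary at 10% is about 4 to 5%.

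**4. Precision of the estimate.** At ρ = 10% the SD is 0.0672 without and 0.0669 with centre (30 centres). The largest difference in any cell is 0.0670 against 0.0666, about 0.6%. Adding centre changes the reported width, not the estimate's precision.

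**5. Effect on decisions.** Largest observed ratio that still passes = margin / 10^(1.963·SE), at the Table 4 SDs.

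- 23F: 1.963 × 0.0764 = 0.150, and 2/10^0.150 = 1.416.
- Anti-gE: 1.963 × 0.35 × 0.0698 = 0.048, and 1.5/10^0.048 = 1.343.
- At ρ = 10%, the simulated width ratio of 0.954 moves these to 1.439 and 1.350. Only an observed ratio inside those narrow bands would be decided differently.

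**The case against.** The strongest reply is that this is a matter of preference. The model is prespecified, identical in Protocol and SAP, and already contains the age strata and each subject's own baseline. Any error works against the sponsor. The centre effect is unknown and there are reasons to expect it to be small: baseline adjustment removes much of what differs between centres, and each assay is run by one organisation's laboratory, blinded to treatment (Protocol 5.3 and 5.8.3). At a 2% share the planned analysis is nominal in every respect.

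All of that stands as a limit on size. It does not explain why a factor used in the allocation and already recorded is absent from the model. Nor does the loss of balance between about 912 minimised and 820 analysed subjects remove the effect, as step 3 shows.

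A further caution also stands. Comparing the two models' interval widths directly suggests an excess of 4.7 to 4.9% at a 10% share. That overstates it, because the random-intercept interval is itself slightly narrow in the simulation (mean SE 0.0664 against an SD of 0.0669). At shares of 2% and 5%, the centre model's one-sided error is no closer to 2.5% than the planned model's.

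**Conclusion.** The omission is real and unexplained, and its consequence is small and conservative. If centre predicts titre beyond baseline and age, the intervals for the 14 ratios are wider than the estimate's true variability warrants: negligibly at an assumed 2% share of residual variance, and about 4 to 5% at 10%. These sizes rest on assumed centre shares, numbers of centres and minimisation probability, none of which the documents give.

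Two stronger readings are tempting. A reader might infer that ignoring a minimisation factor makes the non-inferiority tests invalid or too liberal. It does not: the upper limit moves away from a claim of non-inferiority, and the planned model's simulated one-sided error was 2.57% with no centre effect (within Monte Carlo error of 2.5%) and 2.49%, 2.43% and 2.12% at shares of 2%, 5% and 10%. A reader might also infer that the trial is underpowered. The stated figure of about 91% reproduces from SDs that take no credit for centre, so it is unaffected. A positive conclusion is not threatened. This is a minor improvement at low cost.

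**What to change.** **If immunogenicity results have not been seen:** add centre to both ANCOVAs in SAP 6.3.1.2 and 6.3.2.1 as a random intercept, reducing to the current model if the centre variance is estimated as zero. State the degrees-of-freedom method (for example Kenward-Roger), since the criterion is a confidence limit. Bring the footnotes of Templates 30 and 31 into line. Record the change in SAP section 9 as a departure from Protocol 10.7.2, made because centre is a minimisation factor.

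**Otherwise:** keep the protocol model as primary and specify the centre-adjusted ANCOVAs, before they are run, as a sensitivity analysis outside the fixed sequence. A sentence on why the primary model omits centre belongs with it.

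The first route costs one model term and a documented departure. Protocol 10.10 requires that "Any deviation(s) or change(s) from the original statistical plan outlined in this protocol will be described and justified", and the Family 3 wording was clarified in Protocol Amendment 2 after regulator comments on "the adjustment for baseline titers in the computation of the Multiplex Opsonophagocytosis Assay (MOPA) Geometric Mean Titers (GMT) ratios". With no centre effect the interval width is essentially unchanged (simulated ratio 0.998 to 0.999). The second route costs one extra table. Margins, testing order and other covariates stay as they are.
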